4.5. PK Analysis Set

The PK parameter analysis population is defined as all enrolled patients treated who have sufficient information to estimate at least 1 of the PK parameters of interest. The PK concentration population is defined as all enrolled patients who are treated and have at least 1 analyte concentration.

CCI

4.7. Treatment Misallocations

Subjects who receive the wrong initial dose for whatever reason will be analyzed according to the initial dose actually received. Subjects who receive the wrong dose after the initial dose will be analyzed according to the initial dose received.

4.8. Protocol Deviations

The determination of protocol deviations (PDs) and important protocol deviations (IPDs) will follow Pfizer standard operating procedures. A full list of PDs, IPDs, and IPDs that are excluded from Per-protocol analysis will be determined prior to the database release and be included in the CSR.

5. GENERAL METHODOLOGY AND CONVENTIONS

This is an open-label dose escalation study and the data will be continuously monitored during the study. No formal interim analysis is planned for this study.

5.1. Statistical Hypotheses

There are no statistical hypotheses.

5.2. Statistical Decision Rules

5.2.1. Dose Escalation

The dose escalation in Part 1A will start with Accelerated Titration Design (ATD) as proposed by Simon et al². Part 1 will have an initial accelerated phase followed by a standard (mTPI) escalation phase. During the accelerated phase, initial cohorts to contain a minimum of one patient until the first instance of first-cycle CTCAE grade ≥ 2 toxicity.

The traditional mTPI design⁵ uses a Bayesian statistics framework and a beta/binomial hierarchical model to compute the posterior probability of 3 dosing intervals that reflect the relative difference between the toxicity rate of each dose level to the target rate ($pT = 0.275$). If the toxicity rate of the currently used dose level is far smaller than pT , the mTPI will recommend escalating the dose level; if it is close to target probability (pT), the mTPI will recommend continuing at the current dose; if it is far greater than pT , the mTPI will recommend de-escalating the dose level. These rules are conceptually similar to those used by the 3+3 design, except the decisions of an mTPI design are based on posterior probabilities calculated under a coherent probability model. The proposed mTPI method for this protocol includes stopping rules and dose escalation criteria, which prevents the target DLT rate to reach $\geq 33\%$ for determining the MTD. This proposed mTPI method is more conservative than the traditional TPI method.

Decision rules are based on calculating unit probability mass (UPM) of 3 dosing intervals corresponding to under, proper, and over dosing in terms of toxicity. Specifically, the underdosing interval is defined as $(0; pT - e1)$, the over-dosing interval $(pT + e2, 1)$, and the proper-dosing interval $(pT - e1, pT + e2)$, where $e1$ and $e2$ are small fractions. Therefore, the target interval for the DLT rate is $(0.225, 0.325)$.

The 3 dosing intervals are associated with 3 different dose-escalation decisions. The underdosing interval corresponds to a dose-escalation (E), overdosing corresponds to a dose de-escalation (D), and proper dosing corresponds to remaining at the current dose (R). Given a dosing and a probability distribution, the unit probability mass (UPM) of that dosing interval is defined as the probability of a patient belonging to that dosing interval divided by the length of the dosing interval. The mTPI design calculates the UPMs for the 3 dosing intervals, and the one with the largest UPM informs the corresponding dose-finding decision, which is the dose level to be used for future patients. For example, if the under-dosing interval has the largest UPM, the decision will be to escalate, and the next cohort of patients will be treated at the next higher dose level. Ji et al. (2010)⁵ have demonstrated that the decision based on UPM is optimal in that it minimizes a posterior expected loss (ie, minimizes the chance of making a wrong dosing decision).

5.2.2. MTD Determination

This study contains dose escalation with single agent (Part 1A) in patients with advance or metastatic solid tumor, and a combination dose escalation with enzalutamide in previously treated patients with mCRPC (Part 1B). Part 1A and Part 1B will determine the MTD/RP2D in sequential dose escalation cohorts.

The dose finding process in the current study is designed to establish the MTD defined as the highest dose that yields a target of approximately 27.5% probability of DLT and considers equivalent doses that yield probability of DLT in the interval (Equivalence Interval) of (22.5%, 32.5%). Note the DLT rate for cardiac toxicity should not exceed 10%. The 27.5% target was chosen based on safety considerations. The prior distribution of DLT is set as a beta (0.5,0.5) and the threshold probability for early termination and dose exclusion is set to 0.95 as suggested in the original mTPI method (Ji et al., 2010).⁵ Similarly, doses with an incidence of DLT, eg 4 out of 10, or apparently higher than 32.5% cannot be selected as MTD, even though it might be allowed by the mTPI method.

Cohorts of patients could receive doses already tested but a dose that is associated with decision to “dose de-escalate, unacceptable toxicity” cannot be revisited and no more patients should be treated at this dose or higher doses for the remainder of the trial.

The maximum sample size for Part 1A would be approximately N=40 for the monotherapy dose escalation and approximately N=20 for the combination dose escalation, but actual sample size will depend on the underlying dose toxicity profile and variability in actual data realization.

The study will continue accruing until one of the three stopping conditions below is triggered.

- The maximum sample size has been achieved (approximately 40 patients in Part 1A monotherapy dose escalation, approximately 20 patients in Part 1B combination dose escalation, and 10 patients in Part 2A monotherapy dose expansion and 20 patients in Part 2B combination dose expansion);

- 6 - 12 patients that have been enrolled at a dose level that is predicted to be the MTD per the mTPI method;
- All dose levels explored appear to be overly toxic, and the MTD cannot be determined.

Due to binomial data variability in small samples, DLTs may be observed in a first cohort(s) by chance even when the true Probability (DLT) is fairly low. This could result in the estimated posterior DLT rate to exceed the targeted 27.5% very early in the trial.

The following table shows the probability of escalating to the next dose level for a range of underlying true DLT rates. For example, for a DLT that occurs in 10% of patients, there is a greater than 90% probability of escalating. Conversely, for a DLT that occurs with a rate of 70%, the probability of escalating is 3%. It is assumed that dose escalation occurs with either 0/3 or 1/6 patients with DLTs.

Probability of Escalating Dose

True underlying DLT rate	10%	20%	30%	40%	50%	60%	70%	80%	90%
Probability of escalating dose	0.91	0.71	0.49	0.31	0.17	0.08	0.03	0.009	0.001

5.2.3. Sample Size Determination

Part 1

In Part 1, patients will participate in a dose escalation phase aimed at estimating the MTD. The sample size for this component of the study will vary depending on the number of DLTs observed.

A maximum of 60 patients are expected to be enrolled in the dose escalation safety cohorts in Part 1, including approximately 40 patients for the monotherapy dose escalation and approximately 20 patients for the combination dose escalation. The actual number of patients enrolled will depend on the tolerability of PF 06952229 and the number of dose levels required to identify the MTD/RP2D. It is expected that the dose escalation process can be stopped and MTD declared with approximately 6 to 12 patients at the MTD dose. As for the number of patients treated at each dose, it is expected to be at 1 to 4 patients for the doses actually studied. However, since variable cohort size is allowed, the actual number of patients treated at each dose (including MTD) will vary from 1 to 12 patients.

Part 2

For PF 06952229 single agent expansion in patients with mCRPC, the planned sample size of the expansion cohort is 10 based on clinical consideration.

PF 06952229 single agent in combination with enzalutamide for patients with metastatic castration resistant prostate cancer (mCRPC), assuming a sample size of 20, and the observed PSA50 response is 60% (12/20), the Bayesian posterior probability to demonstrate that the "True PSA50 response" is greater than 37% is 98.15%. Assuming 80% of the 20 patients have measurable disease and are response evaluable (16 patients evaluable), and

the observed ORR is 43.75% (7/16), the Bayesian posterior probability to demonstrate that the "True ORR" is greater than 30% is 86.89%.

All the Bayesian calculations above assume a non informative Uniform (0,1) prior.

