9.6. Sample Size Determination

9.6.1. Part 1

In Part 1, patients will participate in a dose escalation phase aimed at estimating the MTD. The sample size for this component of the study will vary depending on the number of DLTs observed.

A maximum of 60 patients are expected to be enrolled in the dose escalation safety cohorts in Part 1, including approximately 40 patients for the monotherapy dose escalation and approximately 20 patients for the combination dose escalation. The actual number of patients enrolled will depend on the tolerability of PF-06952229 and the number of dose levels required to identify the MTD/RP2D. It is expected that the dose escalation process can be stopped and MTD declared with approximately 6 to 12 patients at the MTD dose. As for the number of patients treated at each dose, it is expected to be at 1 to 4 patients for the doses actually studied. However, since variable cohort size is allowed, the actual number of patients treated at each dose (including MTD) will vary from 1 to 12 patients.

9.6.2. Part 2

For PF-06952229 single agent expansion in patients with mCRPC, the planned sample size of the expansion cohort is 10 based on clinical consideration.

PF-06952229 single agent in combination with enzalutamide for patients with metastatic castration-resistant prostate cancer (mCRPC), assuming a sample size of 20, and the observed PSA50 response is 60% (12/20), the Bayesian posterior probability to demonstrate that the "True PSA50 response" is greater than 37% is 98.15%. Assuming 80% of the 20 patients have measurable disease and are response evaluable (16 patients evaluable), and the observed ORR is 43.75% (7/16), the Bayesian posterior probability to demonstrate that the "True ORR" is greater than 30% is 86.89%.

All the Bayesian calculations above assume a non-informative Uniform (0,1) prior

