5.3.2. Analyses for Binary Data

Binary endpoints in this study include ORR, complete response (CR), and partial response (PR). Response assessment will be based on PCWG2 for prostate cancer patient, and will use RECIST 1.1 for other tumor types. If deemed necessary disease control rate (ie, DCR, which is defined as the proportion of patients that achieved CR, or PR, or stable disease) may also be calculated for Part 2. Descriptive statistics along with the corresponding 2-sided 95% confidence intervals using an exact method will be provided for these endpoints.

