6.3. Analysis for Secondary Endpoints

6.3.1. Efficacy Endpoints Analysis

ORR, as assessed using PCWG2 for prostate cancer and RECIST version 1.1 for other tumor types, is a key efficacy endpoint. The following analyses will be performed in the mITT population by tumor type and pooled:

The ORR, along with other efficacy analyses will be performed in the mITT population. Part 1 and Part 2 data will be summarized separately, and may also be pooled together for analysis if deemed necessary. Specifically, the key tables in Part 2 include:

1. ORR by visit: investigator provided tumor response CR, PR, and CR+PR will be presented by descriptive statistics (frequency and percentage) and 95% confidence interval.
2. Best overall response of CR, PR, and CR+PR. This will include best overall response derivation without confirmation and with confirmation. Descriptive statistics (frequency and percentage) and 95% confidence interval will be provided.

Tumor response data in Part 1, Part 2 and across the two Parts may be summarized with descriptive statistics (frequency and percentage) in the following groups by visit and then best overall response across all visits:

- Overall summary for all doses and all tumor types;
- By tumor type regardless of dose;
- By dose regardless of tumor type;
- By dose and tumor type if data permit.

Summary tables of best overall response rate, PFS, OS, DOSD, and DOR may be provided by the groups aforementioned when deemed necessary (eg, if there are ≥ 5 patients in a specific group).

In addition, PSA50 Response Rate defined as $\geq 50\%$ PSA reduction from baseline assessed by PCWG2 for prostate cancer patients will be summarized similarly as ORR. See [Section 9.5](#) for more details on PSA measurement.

Efficacy listings (tumor measurements listings and tumor response listings) will be provided that include the investigator provided tumor measurement data, tumor response, best overall response, first CR/PR date, last date with CR or PR, most recent date without progression, progression date, death date, and last tumor assessment date, etc.

Endpoint	Analysis Set	Statistical Method	Model/Covariates/Strata	Missing Data
Overall response	mITT	Exact CI	See aforementioned summary descriptions on data pooling across dose and tumor type	Observed case
Overall Survival	ITT	Kaplan-Meier	See aforementioned summary descriptions on data pooling across dose and tumor type	Censored at last visit

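### Part 2B's N=20 rests on posterior probabilities that no planned analysis reports, and the printed values do not match the stated Uniform(0,1) prior

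*SAP*

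**What the plan says.** **Sizing.** SAP 5.2.3 and Protocol 9.6.2 carry the same paragraph for Part 2B. Starting from "assuming a sample size of 20" and 12 PSA50 responders, they state that "the Bayesian posterior probability to demonstrate that the 'True PSA50 response' is greater than 37% is 98.15" percent. They then take 16 of the 20 patients as response-evaluable with 7 responders, and give 86.89% as the posterior probability that true ORR exceeds 30%. The protocol adds: "All the Bayesian calculations above assume a non-informative Uniform (0,1) prior". The SAP says the same. No other argument for N=20 is offered, and neither document gives a source for 37% or 30%.

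**Analysis.** SAP 5.3.2 names ORR, CR and PR as binary endpoints and says: "Descriptive statistics along with the corresponding 2-sided 95% confidence intervals using an exact method will be provided for these endpoints". PSA50 is not in that list, but SAP 6.3.1 says that the PSA50 rate "for prostate cancer patients will be summarized similarly as ORR", so it inherits the same treatment. The method table in SAP 6.3.1 lists an exact CI for overall response. Protocol 9.3 says only that response rates will be summarized if the data allow. None of these sections mentions a posterior probability, a prior for response, or the 37% and 30% reference rates. The Bayesian model in SAP 5.2.1 and 5.2.2 concerns DLTs only.

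**Status.** Protocol section 2 lists PSA50 among the Part 2B primary endpoints, under an objective to estimate efficacy. SAP 5.1 states that there are no hypotheses.

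**The concern.** A sample-size rationale should describe what the planned analysis will deliver. Here the rationale is a Bayesian statement about two reference rates, and the analysis is a frequentist interval with no reference rate. A team that follows the SAP exactly will never produce the quantity that justified 20 patients.

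This matters most at the plan's own illustration. With 12/20, the sizing text speaks of demonstrating a PSA50 rate above 37%. The tabulated interval could have a lower limit just below or just above 37%, depending on an exact method that the SAP leaves open. If the posterior is not pre-specified and the interval is not named, the choice between these summaries would be made after the data are seen. Adding the posterior later would be an unplanned exploratory analysis under SAP 5.3.

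The word *demonstrate* also invites a reading as power, although the figure is conditional on 12/20 having been observed. And if the printed posteriors do not follow from the stated prior, nobody running the planned analysis would find out.

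**Working it through.** **Inputs** (SAP 5.2.3): n=20, x=12, reference 37%; n=16, x=7, reference 30%; prior Uniform(0,1), which is Beta(1,1). From SAP 5.3.2: two-sided 95% exact interval, method not named.

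**Step 1: reproduce the printed posteriors.** With prior Beta(a, b) the posterior is Beta(a+x, b+n−x), and P(rate > p0) = 1 − F(p0), where F is the posterior distribution function.

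| Prior | PSA50 posterior | P(>37%) | ORR posterior | P(>30%) |
|---|---|---|---|---|
| Beta(1,1), as stated | Beta(13,9) | 98.21% | Beta(8,10) | 89.54% |
| Beta(0.5,0.5) | Beta(12.5,8.5) | 98.18% | Beta(7.5,9.5) | 88.29% |
| Beta(0,0) | Beta(12,8) | 98.15% | Beta(7,9) | 86.89% |
| Printed | | 98.15% | | 86.89% |

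The stated prior misses the printed values by 98.21 − 98.15 = 0.06 points for PSA50 and 89.54 − 86.89 = 2.65 points for ORR. Beta(0,0) matches both to the printed precision, as if the prior counts had not been added.

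**Step 2: the interval the SAP would report.** Clopper-Pearson limits are the 2.5% quantile of Beta(x, n−x+1) and the 97.5% quantile of Beta(x+1, n−x).

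- 12/20: Beta(12,9) gives 36.05% and Beta(13,8) gives 80.88%. The interval includes 37%, by 37 − 36.05 = 0.95 points.
- 7/16: Beta(7,10) gives 19.75% and Beta(8,9) gives 70.12%. The interval includes 30%.

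As a check, P(X ≥ 12 | n=20, p=0.37) = 3.08%. This exceeds 2.5%, so 37% must lie inside the Clopper-Pearson interval. The first count that excludes 37% is 13/20, with a lower limit of 40.8%.

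**Step 3: does the exact method matter at 12/20?** Yes. Blaker's exact interval also includes 37% (its two-sided value at 37% is 0.061, above 0.05). The minimum-likelihood exact interval starts at 37.2% and excludes it.

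**Step 4: the Bayesian interval for comparison.** Under Uniform(0,1) the equal-tailed 95% credible intervals are 38.4% to 78.2% for 12/20 and 23.0% to 67.1% for 7/16. For PSA50 the credible interval excludes 37% and Clopper-Pearson narrowly does not. For ORR both intervals include 30%.

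**The case against.** The strongest reply is that nothing can fail here. SAP 5.1 states no hypotheses, the Part 2B efficacy objective is to estimate, and an exact interval suits estimation. Sizing a Phase 1 expansion cohort by illustration and reporting it descriptively is ordinary practice. The posterior is also a closed-form function of the reported counts, so a reader can derive it, and SAP 5.3 allows extra exploratory analyses.

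Most of this stands, and it rules out four stronger readings that a reader might infer.

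- *12/20 is a success case that misses its own criterion.* The documents present 12/20 as an assumed observation. No section requires an interval to exclude 37% or 30%.
- *The interval contradicts the posterior.* The estimate is 60% and the lower limit is under one point below 37%. The exact one-sided tail is 3.08% and the posterior tail is 100 − 98.21 = 1.79%. Both favour a rate above 37%. They part only at a 2.5% cut-off that the plan never adopts.
- *The ORR example shows the same disagreement.* It does not. A posterior of 87% to 90% already implies that a two-sided 95% interval will contain 30%.
- *98.15% overstates the chance of success.* If the true rate were 60%, the chance of at least 12/20 would be 59.6%, and of at least 13/20, 41.6%. Those are probabilities of data given an assumed rate, whereas 98.15% is a probability about the rate given data. The plan assumes no true rate, so the comparison shows no error.

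The reply does not answer two things. The sizing quantity is absent from the pre-specified analysis. And a reader who derives it under the stated prior will not obtain the printed ORR figure.

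**Conclusion.** The point holds as a mismatch between the sizing rationale and the planned analysis, together with an internal inconsistency in the printed figures. N=20 is supported only by two posterior probabilities, and the SAP plans neither. At 12/20 the Clopper-Pearson interval of 36.1% to 80.9% includes 37% by about one point. That detail depends on a method that the SAP does not name, so it argues for naming the method, not for calling the cohort too small. Under the stated Uniform(0,1) prior the figures should read 98.21% and 89.54%. The PSA50 difference is negligible; the ORR figure is 2.65 points too low.

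This rests on three assumptions. The exact CI for PSA50 is inferred from SAP 6.3.1 treating it like ORR. The denominators are 20 and 16 as in the sizing text, although SAP 6.3.1 analyses the mITT population, which could differ. The attribution to Beta(0,0) is inferred from the match on both figures, since the documents do not show the calculation.

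**What to change.** 1. In SAP 5.3.2 and 6.3.1, for Part 2B, pre-specify the posterior probability that PSA50 exceeds 37% and that ORR exceeds 30% under the Uniform(0,1) prior, each with a 95% credible interval, beside the exact confidence interval. Name the exact method, for example Clopper-Pearson.
2. In SAP 5.2.3 and Protocol 9.6.2, restate the figures as 98.2% and 89.5% under Uniform(0,1), or correct the stated prior and use that same prior in item 1. Without this, the new analysis would return 89.5% for the data for which the sizing text prints 86.89%.
3. In the same paragraphs, drop the language of demonstrating. Describe each figure as the posterior probability, given an observed 12/20 (or 7/16), that the true rate exceeds 37% (or 30%). State beside it the Clopper-Pearson 95% intervals those results would give: 36.1% to 80.9% and 19.8% to 70.1%.

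The cost is SAP wording, two closed-form calculations, one extra table row and a short protocol edit at the next amendment. No patients or design features change. The only downside is that the stated figures shift slightly.

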5.3. General Methods

Whilst every effort has been made to pre-specify all analyses in this statistical analysis plan, if any additional exploratory analyses are found to be necessary, the analyses and the reasons for them will be detailed in the clinical study report (CSR).

Unless otherwise specified, the baseline value is defined as the value collected at the time closest to, but prior to, the start of study drug administration in the first cycle. All data will be categorized based on the scheduled visit at which it was collected. These visit designators are predefined values that appear as part of the visit tab in the eCRF.

5.3.1. Analyses for Time to Event Data

Time to event endpoints in this study may include progression-free survival (PFS), duration of response (DOR), time to response (TTR), time to progression (TTP), and overall survival (OS). These endpoints will be summarized using the Kaplan-Meier method⁶ and displayed graphically when appropriate. Median event times and 2-sided 95% confidence intervals for time-to-event endpoint (Brookmeyer and Crowley, 1982)⁷ will be provided.

5.3.2. Analyses for Binary Data

Binary endpoints in this study include ORR, complete response (CR), and partial response (PR). Response assessment will be based on PCWG2 for prostate cancer patient, and will use RECIST 1.1 for other tumor types. If deemed necessary disease control rate (ie, DCR, which is defined as the proportion of patients that achieved CR, or PR, or stable disease) may also be calculated for Part 2. Descriptive statistics along with the corresponding 2-sided 95% confidence intervals using an exact method will be provided for these endpoints.

